### **5.5.2. Premature Study Discontinuation**

A participant may withdraw or be withdrawn from the study if any of the following occurs:

- Pregnancy of study participant
- Failure by the participant to attend multiple clinic visits
- Failure to receive the first HXTc infusion
- Failure to continue to meet pre-dose safety assessment requirements
- Failure to meet baseline IUPM measurement criteria
- Development of an illness that requires treatment with certain medications not allowed in this study
- Inability to manufacture HXTc product for infusion

- Poor adherence to ART as judged by the PI (or designee)
- Request by the participant to withdraw
- Request of the participant's primary care provider if s/he thinks the study is no longer in the best interest of the participant
- Participant judged by the PI (or designee) to be at significant risk of failing to comply with the provisions of the protocol as to cause harm to self or seriously interfere with the validity of the study results
- At the discretion of the IRB/Ethics Committee, Food and Drug Administration (FDA), NHLBI, Office for Human Research Protections (OHRP), other government agencies as part of their duties, PI, or industry supporter

## 6. STUDY INTERVENTION

### 6.1 HXTC

#### 6.1.1. Collection of 100 mL of Blood

Participants will have 100 mL of blood drawn at Step 3, Visit 5 to make the study product. These whole blood samples are shipped ambient temperature overnight to the CETI Processing Facility at CNH in Washington, DC. This shipment also includes an additional sample for HLA analysis.

If the participant previously participated in another study protocol at UNC and has sufficient product already manufactured under IND 15984, the study will not require an additional blood sample and will use the previously manufactured and stored HXTCs.

#### 6.1.2. Study Product Manufacturing

The study product will be made at an established GMP facility at CNH in Washington, DC. A description of the facilities and their operation can be found in the IND 15984 application under IND Section 7.0 – Product Manufacturing & Characterization Manufacturing Environment.

##### 6.1.2.1. Manufacture of HXTC

###### **Cells.**

The cell therapy product for infusion consists of autologous HXTCs targeting the gag, pol, and nef antigens of HIV-1. Blood will be collected by venipuncture and processed according to UNC Clinical and Translational Research Center (CTRC) and shipped ambient to CNH per SOP. Blood will be processed into peripheral blood mononuclear cells (PBMCs) and then used to manufacture three different components: (1) Dendritic cells (DCs) that will be loaded with pepmixes spanning the three target antigens,

irradiated and used as antigen-presenting cells (APCs) for the first stimulation of PBMCs, (2) peptide pulsed autologous T- cell PHA blasts and K562 that will be irradiated and used for the second and subsequent stimulations of HXTCs, and (3) HXTCs generated by stimulation with peptide-pulsed PHA blasts and K562 and which will comprise the final T-cell product.

The flow chart for these procedures is shown in **Figure 2** of the protocol.

**Overlapping Peptide Libraries (pepmixes).** PepMixes HIV Ultra produced by JPT Peptide Technologies will be used as an antigen source. These pepmixes include a pool of 150 15meric peptides derived from Gag, Pol, and Nef polyprotein designed to cover the high sequence diversity of the HIV-1 virus. The pepmixes were derived from protein sequences of all subtypes of HIV-1/SIVcpz based on the HIV sequence database of the Los Alamos National Lab. The end product pool will be cryopreserved prior to infusion.

**Cell Bank System.** A formal cell bank system will not be used for the cell therapy product. Back-up cells will be frozen down at various stages during the manufacturing process. Each final product, however, will consist of a single lot of cells designated for a specific participant.

**Manufacturing Environment.** The cell therapy product described in this section will be manufactured by the Cell Processing Facility (CPF) staff in the Program for CETI at CNH in Washington, DC. These are ISO 7 and ISO 8 manufacturing environments that operate in compliance with current Good Manufacturing Practices as applicable to products intended for Phase I/II clinical trials.

**Dendritic Cell Generation.** The generation and maturation of DCs is accomplished when peripheral blood mononuclear cells are isolated from whole blood and separated by adherence. Monocytes contained in the adherent fraction are cultured in DC skewing conditions for 4- 5 days. They are then matured with an established cytokine cocktail before use as an antigen presenting cell.

**Loading Dendritic Cells With Pepmixes.** Mature DCs are pelleted and pulsed with pepmixes using a proprietary algorithm to provide broad coverage of gag, pol, and nef across all clades.

[figure not shown]
**HXTC generation.** HXTCs are derived from the non-adherent fraction of PBMCs. T cells are stimulated a minimum of two times using Gag, Pol, and Nef pepmix-pulsed DCs for the first stimulation and pepmix-pulsed,

irradiated PHA blast for the second and any subsequent stimulations, if required for HXTC expansion. Genetically-modified co-stimulatory K562 cells (GM-K562) will be incorporated into the co-culture during the second stimulation, if needed based on insufficient expansion.

Culture of DCs and T cells will be performed in the presence of Atazanavir (AZT) and Enfuvirtide (T20) to inhibit potential HIV replication in cultures. At the end of the culture period, HXTCs will be cryopreserved for infusion and submitted for release testing. For information purposes only, additional assays such as ICS, elispot, and pentamer analysis will be performed based on cell availability and HLA.

Each product will have 4 identifying IDs. All labeling will conform to the labeling procedures required by CETI. All cultureware is labeled with the UNC participant ID (PID) and Study ID (SID) as well as the unique CETI-assigned donor identification number (DIN) and unique product number (P number). Only one participant cell line is ever processed at any one time. Medium prepared and labeled specifically for each participant's cells is always used.

**Figure 2: Summary of Manufacturing Process**

#### 6.1.3. Cryopreservation of Products

When sufficient cells for participant infusion are obtained, they are characterized and frozen. The number of cells required for five participant doses is based on the participant's body surface area. Sufficient cells to allow for loss during

cryopreservation (+ up to 20%) and for samples required for characterization and safety testing are processed. The product's cells and supernatant will be tested for mycoplasma testing and microbiological testing. Final product will be tested for HLA-typing, and phenotyping, and viability. The final cell suspension will also undergo endotoxin testing. Cryovials or cryocyte bags are labeled with participant's PID, SID, CETI DIN, and P number, type of component, number of cells, and date of freezing. Cryovials or bags are then cryopreserved in a controlled rate freezer and transferred to storage in the Central Processing Facility liquid nitrogen freezer under the auspices of QC (quality control). The storage facility is within clean room space and is fully monitored 24/365.

#### 6.1.4. Study Product Manufacturing Process

**Reagents.** Certificates of analysis for all reagents, materials, and supplies are kept on file indefinitely and the lot numbers, manufacturer, and expiration date of each is captured at each use by means of our inventory control system where only released supplies and reagents are available in the GMP facility, and all supplies and reagents are tracked on the worksheet.

**Reagent Qualification.** Pepmixes are a mixture of peptides chosen by a proprietary algorithm developed by JPT Peptide Technologies to provide broad coverage of HIV antigens Gag, Pol, and Nef across many clades of HIV. JPT Peptide Technologies will provide these clinical grade pepmixes freeze-dried. One mg of each individual peptide was synthesized and purified by HPLC to a purity of  $\geq 90\%$  measured at 220nm using a linear gradient system. The purity and identity of the peptides was confirmed by high-performance liquid chromatography (HPLC) and mass spectroscopy (LC-MS). For pooling, sub-pools of 10-25 peptides were generated. The presence of all peptides within sub-pools was proven by LC-MS analysis of each sub-pool. From each sub-pool at least one peptide was defined as a "marker-peptide" having a unique molecular weight and HPLC retention behavior. Sub-pools were combined and the generated final pool applied to LC-MS. LC-MS data were tracked to show the presence of at least one "marker-peptide" per sub-pool within the final pool confirming that all individual peptides are present in the final pool. The pepmixes are sterile, and endotoxin-free.

Materials and reagents in contact with the product during manufacturing are sterile and pyrogen-free as determined from the manufacturer's certificate of analysis. No antibiotics are used during manufacturing. Records of all testing are kept on file.

**Removal of Reagents from Final Product.** Cytokines, antiretrovirals, and culture medium are removed by extensive washing of the cells. The final cells are washed four times and re-suspended in balanced salt solution or plasmaLyte containing US Pharmacopeia (USP) human serum albumin and USP dimethyl sulfoxide (DMSO) for cryopreservation.

**Antibiotics:** Antibiotics are not used during manufacturing.

#### 6.1.5. Product Testing and Release

##### **Test Methods**

The following tests are performed by the CETI QC laboratory or a CNH facility per standard operating procedures.

##### ***Sterility Testing***

The BacT/Alert blood culture system and Fungal Isolator tubes are used to test sterility of the final product, and samples are inoculated into culture medium in anaerobic, aerobic, and fungal culture bottles. Bottles are incubated for 14 days (bacterial) or 21 days (Fungal) with ongoing assessment for contamination.

##### ***Mycoplasma***

Mycoplasma testing of the final product uses a commercially available MycoAlert (Lonza) by the CETI Quality Control Laboratory. This assay uses the MycoAlert kit, which detects the presence of mycoplasmal enzymes, which catalyze the conversion ADP to ATP and is detectable using luciferase. It is used for in-process testing and to obtain rapid results while results of the culture assays are pending. Data from this test method will be accumulated in preparation for validation against the Points to Consider method.

##### ***Endotoxin***

Endotoxin levels in the final product will be assayed using the Limulus Amebocyte Lysate assay. For release testing, the Endosafe PTS system will be used. This test is a miniaturized version of the standard LAL assay and the cartridges employed have received FDA approval. The limit of quantitation of the assay is approximately 0.05 EU/mL.

##### ***Identity***

The identity of the cells will be determined by HLA typing. The final product consists of participant-derived HIV-specific T cells. Therefore, the HLA type of the final product should be identical to that of the participant blood.

##### ***Potency***

For this phase I study, potency is not a release criterion. However, for safety purposes we will ensure that the immunophenotype excludes the presence of dendritic cells (CD3-CD83+) and GM-K562 cells (CD3-, CD16/56-, CD32+, CD83+) in the product. For informational purposes, the potency of all HXTCs will be evaluated using cytotoxicity and or Elispot assays.

### ***Viability***

Viability of the final cell product will be assessed for release using trypan blue exclusion.

### ***Notification of Physician in Case of Positive Sterility Report***

The final cell product will be tested for sterility using a BacT/Alert test but will not be available at the time the product is released. Should the BacT/Alert or fungal sterilities be reported as positive after product administration, the UNC Principal Investigator and study team will be immediately notified. CETI will obtain and inform him/her of the identity and antibiotic sensitivity of the organism. CETI will generate a Variance to document and determine corrective actions and their efficacy.

**Table 2.** Final product testing

Testing	Test to be used	Specificity/ Sensitivity	Criteria for Acceptance	Results Available Before Administration
Viability	Trypan Blue	Live cells	>70%	Yes
Sterility	BacT/Alert	Bacteria	Negative at 4 days (cultured for up to 14 days)	Yes
Sterility	Isolator tubes Fungal Culture	Fungus	Negative at 4 days (cultured up to 21 days)	Yes
Mycoplasma	MycoAlert	12 most common species	Negative	Yes
Purity Endotoxin	Endosafe PTS (LAL)	<5.0 EU/kg	<5.0 EU/mL	Yes
Identity	HLA Typing	N/A	Identical to participant	Yes
Phenotype	Flow Cytometry	Cell type	<0.1% CD3-, CD16/56-, CD32+, CD83+ (GM-K562 cells); <2% CD3-/CD83+(DCs)	Yes

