#### **6.1.7. Dosage, Preparation, and Administration of HXTC**

Each dose of HXTC is  $1 \times 10^8$  cells/m^2 and each participant will receive five infusions at this dose, provided there are enough manufactured T-cells. If unable to manufacture enough cells for five infusions at  $1 \times 10^8$  cells/m^2 participants will receive five infusions at a dose  $\geq 5 \times 10^7$  cells/m^2 up to  $1 \times 10^8$  cells/m^2 as determined by the protocol team.

The first HXTC infusion (HXTC #1) will be infused approximately 6 hours after the 1st dose of VOR (Step 4, Visit 7) and the 2nd HXTC infusion (HXTC #2) after the 6th dose of VOR (Visit 10) in Step 4. In Step 5 each participant will receive the next three HXTC infusions. The 3rd HXTC infusion (HXTC #3) will be infused approximately 6 hours after the 11th dose of VOR 400 mg (Step 5, Visit 14) and HXTC infusion #4 will occur approximately 6 hours after the 16th dose (Step 5, Visit 16). The 5th or last HXTC infusion (HXTC #5) occurs 1 to 3 days after the 20th dose of VOR (Visit 19).

In preparation of each HXTC dose of  $1 \times 10^8$  cells/m^2, an extra - volume (1 – 20%) is added to account for cell loss. When possible, CETI will cryopreserved the cells at  $1 \times 10^8$  T cells per mL, allowing the cells to be thawed and injected directly. However, the cell concentrations can vary from time to time; therefore, dosage calculations and body surface area (BSA) are calculated both at CETI (prior to shipment) and then by two independent licensed practitioners at the UNC site prior to administration to confirm accurate dose delivery.

The required amount of HXTCs for the infusions are shipped to the UNC HPC Lab, where they are stored and maintained in biological safety cabinets (BSC). If extra cells are produced, CETI archives these aliquots at their manufacturing site. These stored aliquots are accessible for additional infusions under IND 15984 or research analysis.

All study HXTC infusion visits occur in the UNC CTRC. After completion of all required clinical assessments prior to the infusion, the HXTC product is thawed, delivered and verified with the study coordinator. Review of the HXTC product occurs prior to administration per the UNC HIV Cure Center SOP entitled Cellular Product Infusion Guidelines and Emergency Management Plan.

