**7.4.2. Inability to manufacture HXTC therapy or failure to meet release criteria**

In the unlikely event that product or sufficient product is not successfully manufactured for participants, these participants would not proceed to Step 4 and would not undergo any further study procedures.

These participants may undergo a single repeat blood draw of 100mL to allow a second attempt at manufacturing product.

If the participant refuses to repeat the blood draw or the product cannot be manufactured after receipt of the 2nd 100 mL sample, the participant will be terminated from the study. The SID for this participant will be retired and will not be used again. These participants will be replaced in the study.

**7.4.3. Inability to meet the pre-dose lab guidelines for study progression based on clinical evaluations at Step 3, Visit 7 and at Step 4, Visit 13.**

If a participant's failure to move to Step 4 or Step 5 is due to an inability to meet one of the pre-dose safety laboratory assessments parameters, repeat the failed criteria one time only.

Participants failing to advance to Step 4, without receiving any combination treatment of VOR and HXTC, will terminate from the study. The SID for this participant will be retired and will not be used again. These participants will be replaced in the study.

Participants completing combination dosing in Step 4 and/or Step 5 who then fail to meet safety assessment requirements, will not receive further doses of VOR or HXTC. Participants will proceed to complete the early discontinuation visit per Step 6, Visit 23 (when clinically acceptable, per PI assessment) and continue to complete the longitudinal assessment at Visit 24.

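### Table 2 accepts a frozen HXTC lot on a day-4 negative culture, and no visible section requires the completed 14-day and 21-day reads before infusion 1 (minor, patient safety)

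*Combined protocol and SAP*

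**What the plan says.** **Sterility testing (Section 6.1.5).** "Bottles are incubated for 14 days (bacterial) or 21 days (Fungal) with ongoing assessment for contamination".

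**Table 2, acceptance criteria.** Bacterial culture: "Negative at 4 days (cultured for up to 14 days". Fungal culture: "Negative at 4 days (cultured up to 21 days". Both rows carry a Yes in the column on whether results are in hand before administration.

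**Notification paragraph above Table 2.** It says that the BacT/Alert result "will not be available at the time the product is released". It then sets out a contingency, opening "Should the BacT/Alert or fungal sterilities be reported as positive after product administration": the investigator is told at once, is given the organism and its antibiotic sensitivity, and a variance is raised.

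**Product (Section 6.1.2.1).** "At the end of the culture period, HXTCs will be cryopreserved for infusion and submitted for release testing". Each participant's product is a single lot.

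**What stands between the lot and infusion 1:**
- Section 7.3.2.2: Visit 6 is scheduled once manufacturing is verified complete, and its labs are signed off before Visit 7.
- Section 7.3.3: Visit 7 is at most 21 days after Visit 6. No minimum interval is given.
- Section 7.3.3.1.2: the investigator reviews Visit 6 labs and the day's clinical assessments before thawing.
- Section 6.1.7: "Review of the HXTC product occurs prior to administration per the UNC HIV Cure Center SOP". That SOP is not among the documents.
- Section 7.4.2, titled "Inability to manufacture HXTC therapy or failure to meet release criteria", and Section 10.1 refer to release criteria and to release.

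**The concern.** The only sterility criterion that the protocol shows for acceptance is the day-4 read. Every later step either points back to release or lists checks that do not name the final reads. As written, infusion 1 may therefore go ahead while a bacterial or fungal culture can still turn positive, and the notification paragraph provides for that event.

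The product does not force this. It is cryopreserved, the recipients are suppressed on ART, and Section 2.4 says that they gain no direct medical benefit. Section 6.1.4 adds that no antibiotics are used in manufacturing. Notification after a late positive acts only once the exposure has happened. Because there is one lot per participant, a single check before infusion 1 would cover all five infusions.

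Only participant safety is at stake. Sample size, power and endpoints are not affected.

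**Working it through.** The plan gives no figure to reproduce, so the check is day arithmetic.

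**Inputs.** Table 2: acceptance read on day 4, final reads on day 14 (bacterial) and day 21 (fungal). Section 7.3.3: infusion 2 is 15 days after infusion 1, VOR dose 10 is 27 days after it, and Visit 13 is 7 to 14 days after dose 10. Section 4.3: manufacturing takes about 8 weeks (56 days). Appendix A: an entry of 4 to 10 weeks after Visit 5, taken here as the Visit 6 window (days 28 to 70), since the table is broken in the text. Section 10.1: clinical assessment follows release.

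**1. Which infusions can precede a final read.** Let culture day 0 be inoculation of the final product and t the culture day of Visit 7. Table 2 gives t ≥ 4.

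| Infusion | Culture day | Before bacterial read | Before fungal read |
|---|---|---|---|
| 1 | t | t < 14 | t < 21 |
| 2 | t + 15 | never (at least 19) | t + 15 < 21, so t = 4 or 5 |
| 3 to 5 | at least t + 27 + 7 = t + 34, so at least 38 | never | never |

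Infusion 2 would need Visit 7 within a day of the day-4 read. Release, lab sign-off and cryogenic shipment make that implausible, so the realistic exposure is infusion 1 only.

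**2. Added wait under a hold.** Wait = 21 − t: 17 days at t = 4 (the theoretical maximum), 15 at t = 6, 1 at t = 20, and zero from t = 21.

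**3. Does the schedule fix t?** No. The 21 days between Visits 6 and 7 are a maximum. The 8 weeks can be read in three ways, counted in days after Visit 5 with inoculation assumed on the day of freezing:
- The 8 weeks include the completed cultures: day 0 is no later than 56 − 21 = 35. Exposure and wait are both zero.
- The 8 weeks end at freezing: day 0 = 56, day-4 read = 60, bacterial read = 70, fungal read = 77.
- The 8 weeks end at the day-4 read: day 0 = 52, fungal read = 52 + 21 = 73.

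**4. Does a hold fit the existing windows?** Visit 6 cannot precede the day-4 read, because it follows release.
- Freezing on day 56: Visit 6 on days 60 to 70 gives labs 77 − 60 = 17 down to 77 − 70 = 7 days old at the fungal read, inside the 21-day limit.
- Freezing on day 52: Visit 6 on days 56 to 70 gives labs 73 − 56 = 17 down to 73 − 70 = 3 days old.
- Freezing on day F in general: release on F + 4 must be no later than day 70, so F ≤ 66. With Visit 6 on the day of release, labs are (F + 21) − (F + 4) = 17 days old at the fungal read.

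The hold therefore fits both windows if freezing is by about day 66. For a freeze on day 67, release is on day 71 and Visit 6 already falls outside the 10-week limit, with or without the hold.

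**The case against.** **Exposure may be nil.** Section 2.1 says that the manufacturing approach yields a product within one month, while Section 4.3 allows about 8 weeks. If expansion takes about 30 of the 56 days, 26 remain, which is more than the 21-day fungal culture. This is a fair inference but not a settled one. The same one-month figure, with a Visit 6 window opening at week 4 and no minimum gap to Visit 7, also permits an early infusion.

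**The Yes column.** It might mean that final results are in hand before administration, with release and administration at separate times and the notification paragraph as a backstop. The wording allows this. However, the Yes stands beside a criterion met on day 4, and the same section plans for positives after administration. It most naturally refers to the day-4 read.

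**Unseen documents.** The infusion SOP (Section 6.1.7) and the IND manufacturing section (cited in Section 6.1.2) are where a final-read check might sit. This stands: absence from the protocol does not show absence from practice.

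**Existing safeguards.** Table 2 already calls for day-4 cultures, mycoplasma and endotoxin results before administration, and cultures continue afterwards. This stands, and it is one reason why the point is minor.

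A reader might go further and infer that participants are being infused on unfinished cultures, or that the prose and Table 2 contradict each other. The documents support neither. They give no infusion dates relative to culture, and the two texts agree if the result missing at release is the final read.

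**Conclusion.** The point holds as a minor, low-cost safety improvement. The visible protocol permits infusion 1 from the day-4 read onward, and no visible section requires the completed 14-day and 21-day reads first. It is not an error in the plan.

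The gap concerns infusion 1, for t below 21. Whether it ever arises in practice is unknown, because t is not given. The documents also give no contamination or late-positive rate, so the size of the risk cannot be stated. Participants who use HXTCs stored from earlier studies and bypass Visits 5 and 6 (Section 4.3) probably have completed reads already; that is an assumption.

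The scheduling result rests on three further assumptions: inoculation on the day of freezing, Visit 6 no earlier than the day-4 read, and the Appendix A entry read as the Visit 6 window.

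**What to change.** - In Section 6.1.5 and Table 2, keep the day-4 negative for release and shipment, and add that infusion 1 requires negative completed 14-day bacterial and 21-day fungal reads.
- Add the same check to the pre-infusion review in Section 7.3.3.1.2.
- In the notification paragraph, say that the result not available at release is the final read.
- Where freezing is late in the process, place Visit 6 after release but close enough to the fungal read to keep its labs recent. About culture day 14 leaves them 21 − 14 = 7 days old. No visit window changes if freezing is by about day 66; a later freeze needs a later Visit 6.

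**Cost.** Any wait set out under the working, and a protocol amendment, which needs IRB approval (Section 11.2) and submission to NHLBI (Section 11.4). Only participants not yet infused can benefit, and Section 2.1 shows that some were treated under Version 2. If the SOP or IND section already requires the final reads, the change only records existing practice.
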